**1. BRIEF SUMMARY**

Baker's cyst is a common entity in adults who have knee pathologies, having different ways to approach it with different recurrence rates. We will attempt to report the outcome of treating Baker's cysts with ultrasound-guided Platelets-Rich-Plasma injection into the cyst versus ultrasound guided Corticosteroid injection into the cyst with at least 6 months follow-up. We plan on evaluating recurrence rates and persistence of symptoms.

**2. PURPOSE OF STUDY AND BACKGROUND:****I. Purpose:**

To evaluate the long term clinical outcome of Ultrasound-guided Platelets-Rich-Plasma injection versus Ultrasound guided Corticosteroid Injection in Baker's cysts.

**II. Background:**

The treatment of Baker's Cysts are based on its presentation, asymptomatic cysts are currently managed conservatively, symptomatic cysts are treated with joint aspiration and Corticosteroid injection, which have shown according to literature a decrease of the cyst size in approximately two-thirds of patients within 2-7 days but only complete disappearance in approximately 7 %. Ultrasound guided cyst aspiration and Corticosteroid injection are also used with reduction of cyst's size with recurrence in 6 months of 19%. Surgical options to remove the cyst include, Open Resection with a recurrence of 50%, 25% of patients have motion limitation recurrence, 37% have wound healing problems or tense swelling of the calf and 75% of patients have joint pain lasting more than 2 days. Arthroscopic resection, with no recurrence in ultrasound performed 6 and 12 months after procedure, pain lasting more than 3 days in 28% of patients, mild hematoma in 7% of patients and 7% where converted into an open procedure.

There is no study using ultrasound guided aspiration of cysts with platelet-rich-plasma injection (PRP). The rationale for the use of PRP is the belief that the additional platelets will exponentially increase the concentration and release of multiple growth and differentiation factors at the injury site to augment the natural healing process. PRP does not have any described negative side effect due to the fact that it is being prepared from subject's own blood, with no risk of allergy or cross infection, relatively easy for a practiced clinician, and reproducible. Studies have shown no negative side effects from the use of PRP injections since its source is the own patient's blood, there is only one study describing local inflammation after a patellar injection of PRP in a patient with Diabetes type I, probably due to the injection and not the PRP itself, hence we are excluding patients having diabetes or any immunologic deficiency as risk factor. PRP is FDA approved, due to no side effects caused by PRP directly, assuring its safety for clinical use. Steinert et al. shows all the latest studies using PRP in sports medicine, showing effectiveness in the use PRP and no side effects, hence, PRP injections are safe to use in clinical subjects. ,

**III. Study Design:**

Prospective study with Randomized patients into Ultrasound-guided Platelets-Rich-Plasma injection and Ultrasound guided Corticosteroid Injection and at least 6 months follow up at our institution.

**IV. Aims:**

- 1) To evaluate the outcome of baker's cysts with the use of Platelets-Rich-Plasma versus Corticosteroid
- 2) To evaluate the recurrence of baker's cysts treated on each group
- 3) To evaluate complications
- 4) To evaluate side effects

### 3. CHARACTERISTICS OF RESEARCH POPULATION

#### I. *Sample Size Justification:*

Assuming normality of the data, we calculated the statistical power assuming effect size 0.3 that is the difference in proportions of people who change their score in their follow-up. We also assume a standardized normal (Z) distribution for one sided test, we aim to achieve 80 % of the power fixing the type one error (alpha) level at 0.05 and we repeated the calculation under different assumption of score changing proportions at each group.

P1	P2	$\alpha$ ( Type I error )	$1 - \beta$ ( power )	Each Group	Total
0.1	0.4	0.05	0.80	25	50
0.05	0.35	0.05	0.80	21	42
0.01	0.30	0.05	0.80	19	38

From the table, we expect that our study will have an enough power to detect the true difference with at least 80% of probability with 25 samples for each arm even allowing less conservative score change proportions. The sample size determined also accounts for screen failures. The total number of subjects to participate in the study is 50.

#### II. **Gender of Subjects:**

Both men and women will be selected for the study without gender preference

#### III. **Age of Subjects:**

There will be no upper age restriction in this study. No participants under age 18 will be selected.

#### IV. **Racial and Ethnic Origin:**

There is no ethnic preference or restriction for this study

#### V. **Inclusion criteria**

- Patients at least 18 years old.
- Patients with baker's cyst who also present with at least one of the following: swelling, local pain or discomfort, limited range of motion or any other symptom directly caused by the baker's cyst.

#### VI. **Exclusion criteria**

- Patients younger than 18 years old
- Local or Systemic active infection

- Active cancer treatment
- Immunodeficiency
- Diabetes
- Hypersensitivity or allergy to Corticosteroid or Lidocaine

**VII. Vulnerable Subjects:**

We do not anticipate inclusion of vulnerable populations within our study group

**4. METHODS AND PROCEDURES****I. Methods and procedures**

Patients who meet the inclusion criteria and do not meet any of the exclusion criteria will be identified during office hours by the PI and co-investigators. Our research staff will explain the purpose of the study to the patient, and will go over the consent form, to fully inform and answer any questions the subject may have.

After patients accept to participate in the study and are formally enrolled in the study, the same day, patients will be asked the Visual Analogue Score (VAS), demographic information will be collected, along with any associated medical history with special interest in knee pathologies and previous treatments. They will be also classified according to their symptoms by the Rauschning and Lindgren criteria which are used to clinically evaluate the presence of the popliteal cysts, pain, posterior sense of tension in the popliteal fossa and its clinical importance for range of motion reduction. They will also complete the Knee Injury and Osteoarthritis Outcome Score (KOOS) to assess short and long term outcome of knee related conditions.

Rauschning and Lindgren criteria:

Grade 0: absence of swelling and pain, no limitation of range of motion

Grade 1: light swelling or a sense of posterior tension after intense activity, minimal limitation of ROM

Grade 2: swelling and pain after normal activity, ROM limitation less than 20 degrees

Grade 3: swelling and pain even when resting, ROM limitation more than 20 degrees

The Knee Injury and Osteoarthritis Outcome Score (KOOS):

- Pain
- Other Symptoms
- Function in daily living (ADL)
- Function in sport and recreation
- Knee-related quality of life (QOL)

We will blindly set 25 envelopes sealed for each group, and randomly assign one of them to each patient. Patients will then be part of either the Platelets-Rich-Plasma group or the Corticosteroid group.

Platelets-Rich-Plasma group: Patients will be asked to stop taking any type of anti-inflammatory medication from 7 days before the procedure to 2 weeks after. At the moment of the procedure, at CMC, the radiology team will draw 30cc of venous blood from the patient and the blood will be processed with the PRP kit and centrifuged in the SmartPrep PRP machine.. The patient is then scanned prone using a linear 14 or 9 MHz transducer. A 20 Gauge spinal needle is usually employed for purposes of aspiration. We can use sterile saline to confirm needle placement in the cyst in lieu of lidocaine and then inject the PRP by the radiologist.

The procedure will be done without using any local anesthetic to avoid pharmacological interaction with the injected substance. A compression bandage will be placed locally for 7 days. Investigators will monitor any side effect from the injection and treat the patients per standard care, this can include

prescription of analgesics. No remaining biomaterial or any blood sample will be collected or stored for future studies.

It must be noted that the radiology team (technicians and radiologist) in charge of the PRP processing and handling, are well trained in this matter, since they have been using PRP and Harvesttech SmartPrep PRP machine in a weekly and sometimes daily basis, as part of patient's treatment or as part of previous clinical trials. [name], who is one of the Co-investigators, will be the radiologist supervising the study in the radiology department, to minimize any potential risk, and assuring appropriate preparation of the product and execution of the procedure.

**Corticosteroid group:** Patients will be asked to stop taking any kind of anti-inflammatory medication from 7 days before the procedure to 2 weeks after.. The radiology team will draw 30cc of blood from the patient, and this blood will then immediately be discarded out of sight from the patient. The blood does not need to be used for the control group, and none of it will be stored for future use. Blood draw is crucial in this group as it will keep the research activities consistent between the groups and prevent any patient from knowing if they are in the treatment or control group. It is crucial to keep the patient blinded for the study to eliminate any bias in the outcomes.

An ultrasound guided aspiration and triamcinolone (40 mg) diluted with lidocaine without epinephrine and ropivacaine will be used to anesthetize the tissues down to the cyst(including within the cyst for steroid injections). A compression bandage will be placed locally for 7 days. Investigators will monitor any side effect from the injection and treat the patients per standard care, this can include prescription of analgesics.

Both groups will be asked to have a follow up after 3 months and 6 months of the day of the procedure with measurements of the dimensions of the baker's cysts with ultrasound, Visual Analogue Score, and Rauschning and Lindgren criteria and reclassification.

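### Drawing one sealed envelope per patient from a 25+25 pool leaves no trace of a second draw; separately, the fixed total makes late assignments partly guessable to anyone who knows the running tally

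*Combined protocol and SAP*

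**What the plan says.** The only text on how patients are allocated is in section 4.I (Methods and procedures): "We will blindly set 25 envelopes sealed for each group, and randomly assign one of them to each patient". The envelopes are sealed and prepared blindly. The text does not mention a generated sequence, numbering, opacity, an independent holder or opener, a log, or reconciliation of used envelopes.

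The pool matches the sample size in section 3.I, which plans the trial "with 25 samples for each arm" and adds: "The total number of subjects to participate in the study is 50". It also says: "The sample size determined also accounts for screen failures". No rate is given.

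On who decides entry, section 4.I says that eligible patients "will be identified during office hours by the PI and co-investigators". The inclusion criteria (section 3.V) accept swelling, local pain or discomfort, "limited range of motion or any other symptom directly caused by" the cyst.

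Section 4.I describes enrolment, VAS, Rauschning and Lindgren grade and KOOS before the envelope step, but does not make that order a rule. The patient is the only person named as blinded (section 4.I, corticosteroid group). The principal investigator is also the Study Monitor, and study data are reviewed weekly (section 4.III, parts II and IV). A co-investigator is the radiologist supervising the procedures (section 4.I, PRP group).

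**The concern.** Two separate weaknesses bear on concealment of the next assignment.

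1. **Redraw.** Chance enters when an envelope is picked for each patient. No particular envelope belongs to a particular patient, so replacing one draw by another would leave nothing to find afterwards.
2. **Guessing.** With exactly 25 envelopes per arm, each assignment changes the odds for the next one. Someone who counts can predict late assignments better than by a coin toss.

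Either route could let expectations about treatment influence who enters which arm. That matters here because eligibility rests partly on attributing a symptom to the cyst, and the people making that judgement are not described as masked. With 25 patients per arm, a few steered patients could shift the comparison. The analysis section (4.II) plans a descriptive comparison of the groups at baseline but names no covariate adjustment.

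**Working it through.** **Inputs.** Pool of 25+25 envelopes, one picked per patient (section 4.I); 50 patients in total (section 3.I); main-row proportions 0.1 and 0.4 (section 3.I table). The plan states "We also assume a standardized normal (Z) distribution for one sided test" and "we aim to achieve 80 % of the power fixing the type one error (alpha) level at 0.05".

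**The plan's own figure.** With pooled variance under the null and no continuity correction,

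n = [z(0.95)·√(2·p̄·(1−p̄)) + z(0.80)·√(p1(1−p1) + p2(1−p2))]² / (p2−p1)²

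Here p̄ = 0.25, 2·0.25·0.75 = 0.375, and 0.09 + 0.24 = 0.33. So n = (1.645·0.6124 + 0.8416·0.5745)² / 0.09 = 24.7, which rounds up to 25. The other two rows reproduce as 21 and 19. The sample size is not affected by this point; it only fixes the size of the pool.

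**Redraw.** Suppose someone draws once more only when the first envelope is for the unwanted arm.

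- First envelope returned to the pool: 0.5 + 0.5 × 25/50 = 0.75.
- First envelope set aside, at the first patient: 0.5 + 0.5 × 25/49 = 0.755.

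**Guessing.** Assume that the tally is known and the guesser names the arm with more envelopes left. After k draws, of which a came from one arm, the chance of a correct guess for patient k+1 is

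Σₐ [C(25,a)·C(25,k−a) / C(50,k)] × max(25−a, 25−k+a) / (50−k)

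| Patient | Chance of a correct guess |
|---|---|
| 1 | 50% |
| 25 | 55.3% |
| 40 | 61.0% |
| 46 and 47 | 68.0% |
| 48 and 49 | 74.5% |
| 50 | 100% |

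- All 50: 28.95 correct on average, and 28.95/50 = 57.9%.
- First 40: 54.9%, or about 21.95 correct.
- Last 10: 70.0%, or about 7.00 correct.
- Last 5: (68.0 + 68.0 + 74.5 + 74.5 + 100)/5 = 77.0%.
- Excess over chance: 28.95 − 25 = 3.95 patients, of which 7.00 − 5 = 2.00 fall in the last 10.
- Assignments fully determined in advance: 2 × 25/26 = 1.92 on average.

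**What drives the guess rate.** The formula uses only the 25+25 total. A numbered list with the same total gives the same percentages. Blocks of a size known to recruiters are worse: for blocks of 4, (1/2 + 2/3 + 2/3 + 1)/4 = 70.8%, and for blocks of 6, 68.3%.

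**The case against.** The strongest reply is that the documents describe sealed envelopes, blindly prepared, and place consent, enrolment and baseline scores before allocation. That stands, and it limits selection after an envelope has been opened. It does not stop selection based on a guess, nor a redraw, and the order is described rather than required.

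It can also be said that the missing order is inferred from one short sentence. It is an inference, but picking an envelope at random for each patient is what the sentence says, and that method has no fixed order.

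The guess rates deserve more caution, and much of the reply stands:

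- They require knowledge of the tally. The documents do not say that the weekly review is by arm. Without the tally the rate is 50%.
- Even with a perfect tally the gain is about four correct guesses in 50, and it is slight over the first 40 patients. Any fixed 1:1 total makes the last patient certain, which raises the figure for the last five.
- If fewer than 50 are randomised, which the remark about screen failures leaves open, the most predictable draws are never reached. Equal arms are then no longer guaranteed either.

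A reader might infer that the unordered pool is what makes late assignments guessable. It is not: the fixed total does that, and numbering alone would change none of those percentages. A reader might also infer that staff are likely to redraw. The documents give no ground for that.

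**Conclusion.** The point holds as two limited weaknesses in a stated method.

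- The draw from a pool could not reveal a second draw. One redraw would move the chance of a preferred arm from 50% to about 75%. How often this might occur cannot be estimated from the documents.
- The fixed 25+25 total allows 57.9% correct guesses overall, 54.9% over the first 40 patients and 70.0% over the last 10. This assumes that all 50 are randomised and that the recruiter knows the tally. Such knowledge is plausible, because recruiters are not masked, the principal investigator reviews data weekly, and a co-investigator supervises the injections. It is not stated.

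It would go too far to say that no analysis could repair the resulting bias. Baseline scores are described as taken before allocation, so measured imbalance can be examined and adjusted for. That corrects selection only in part, because unmeasured differences remain. The change is worth making before the first enrolment, since concealment cannot be restored later.

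**What to change.** **To close the redraw gap.** Before enrolment, an existing staff member who neither enrols nor assesses patients generates one computer-random sequence and places it in opaque envelopes numbered in order. Envelopes are opened strictly in sequence, with study number and date written on each before opening. The protocol should make it a rule that opening follows recorded consent, eligibility and baseline scores. Opened envelopes are kept for audit.

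**To limit guessing.** Withhold the sequence and the running arm totals from the clinicians who identify patients. The weekly study-data review would then be laid out without arm totals. If blocks are used, vary their sizes and do not disclose them.

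**Cost.** A small preparation task, perhaps an hour of existing staff time (an estimate), and a text amendment. Sample size, visits and treatments are unchanged. The downside is that someone outside enrolment must hold the list. One limit remains: the co-investigator supervising the procedures will see which treatment is given, so totals cannot be fully hidden from that person.

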## SCHEDULE OF EVENTS - CONTROL GROUP (Corticosteroid)

Description	Visit 1 (Baseline)	Visit 2 (12 Week)	Visit 3 (24 Week)
Study Visit Windows			
Informed Consent	x		
Complete Physical & Medical History	x		
Knee Assessment/Brief Exam	x		
Ultrasound	x	x	x
Aspiration and Steroid Injection	x		
Visual Analogue Score	x	x	x
Knee Injury and Osteoarthritis Outcome Score	x	x	x
Rauschning and Lindgren criteria	x	x	x

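### Both arms are asked to stop all anti-inflammatory medication for 21 days, and no visible rule exempts or screens out patients who cannot safely pause such a drug taken for another condition

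*Combined protocol and SAP*

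**What the plan says.** Section 4.I (Methods and procedures) puts a medication stop to each arm.

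- PRP group: "Patients will be asked to stop taking any type of anti-inflammatory medication from 7 days before the procedure to 2 weeks after".
- Corticosteroid group: "Patients will be asked to stop taking any kind of anti-inflammatory medication from 7 days before the procedure to 2 weeks after".

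Neither sentence defines the drug class, gives a reason for the stop or makes an exception.

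The inclusion criteria ask for age 18 or over and a symptomatic cyst. The exclusion criteria cover age under 18, active infection, "Active cancer treatment", "Immunodeficiency", diabetes, and hypersensitivity to corticosteroid or lidocaine. Section 2.II (Background) gives the reason for two of these. After describing one report of local inflammation following a PRP injection, it says "hence we are excluding patients having diabetes or any immunologic deficiency as risk factor".

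On the day of enrolment, once the patient has accepted and been formally enrolled, section 4.I has staff collect demographic information "along with any associated medical history with special interest in knee pathologies and previous treatments". Both schedules of events list "Complete Physical & Medical History" at Visit 1. Allocation is by sealed envelope: "We will blindly set 25 envelopes sealed for each group, and randomly assign one of them to each patient".

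**The concern.** The protocol itself creates this interruption of treatment, so one would expect it to say who should not be asked to make it. Read literally, the request reaches every anti-inflammatory drug a patient takes, whether for the knee or for an unrelated condition. There is no upper age limit, and no criterion excludes conditions for which such a drug may be prescribed long term. If the request is made and followed as written, a patient could go three weeks without treatment needed for something other than the cyst.

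What is at stake is the safety of individual patients. The comparison between arms is not in question, because the same stop is put to both.

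**Working it through.** **Length and reach of the stop**

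- Inputs from section 4.I: 7 days before the procedure and 2 weeks after it.
- Length = 7 + 2 × 7 = 21 days (22 calendar days if the procedure day is counted separately).
- Reach: 25 envelopes × 2 arms = 50 planned patients.
- Patients who take such a drug and cannot safely pause it: not given anywhere, so unknown and possibly zero.

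**Where a safeguard could sit, and what is there**

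| Place | What it provides | Does it exempt or screen? |
|---|---|---|
| 3.V Inclusion criteria | Age and symptomatic cyst | No |
| 3.VI Exclusion criteria | Cancer treatment and immunodeficiency may remove some users of such drugs | Only incidentally; Background ties the diabetes and immune exclusions to a PRP reaction, not to the stop |
| 4.I, medical history | May bring such a drug to light | No rule on what to do then; taken after formal enrolment |
| Schedules of events | History and physical at Visit 1 | No; consent, history and injection share one column, so no separate step is shown for checking the stop |
| 4.III, information to be collected | Concomitant medications by type, dose, frequency and duration | No; no collection time and no decision rule |
| 4.III, adverse events and frequency of monitoring | Events recorded from consent; safety data assessed as they occur | No; detects a flare but does not prevent it |
| 5.I Risks | Injection complications and breach of confidentiality | No; the interruption is not listed |
| 5.II Protection Against Risks | Oral anti-inflammatories allowed in the corticosteroid group | No; they treat side effects of the injection and do not continue existing treatment |

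No row supplies an exemption or a screen.

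**Where a new check has to go**

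Section 3.I sets the total at 50 and says that figure already allows for screen failures. The main row of its table can be reproduced from P1 = 0.1, P2 = 0.4, one-sided alpha 0.05 and 80% power, with pooled variance and no continuity correction:

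n = [1.645 × √(2 × 0.25 × 0.75) + 0.842 × √(0.1 × 0.9 + 0.4 × 0.6)]² / 0.3²
= (1.007 + 0.483)² / 0.09 ≈ 24.7, rounded up to 25 per arm.

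The medication stop does not change this figure. It does bear on where the check is placed. The 25 per arm is the formula's own answer, with nothing visibly added. If a patient is enrolled, then excluded at the history, and still counts towards the 50, fewer than 50 are randomised. A patient excluded before enrolment uses 0 of the 50 places and 0 of the 50 envelopes.

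**The case against.** The strongest reply is that this is a request handled by clinicians. Investigators identify the patients, take a full history and record concomitant drugs, and nothing makes stopping a condition of taking part or asks anyone to act against medical advice. The plan never defines the drug class. If ordinary painkilling anti-inflammatories are meant, the hazard shrinks considerably, and serious harm depends on a broad reading that includes drugs the documents never mention. The plan identifies no affected patient. The consent form, where advice on stopping medicines would naturally appear, cannot be seen.

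Most of this stands, and it is why the weight is low. It does not remove the point. The wording in both arms is unqualified and so supports the broad reading, a request from a study team is made in order to be followed, and clinical judgement is not written down as a step that can be checked. A warning in the consent form would still not be an eligibility rule.

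Three stronger readings are tempting, and the documents support none of them.

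- A reader might infer that patients must stop needed treatment. The text only asks them to.
- A reader might infer that patients are not warned. The silence in the Risks section is weak evidence of that while the consent form is unseen.
- A reader might infer a bias between arms, especially as side-effect treatment with oral anti-inflammatories is mentioned only for the corticosteroid group. That provision concerns reactions to the injection. The stop itself is the same in both arms.

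It is also fair to object that preferring exclusion to continuation is partly a matter of judgement, since the plan gives no purpose for the stop. That is accepted, and the alternative is set out with the fix.

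**Conclusion.** The point holds as a low-weight patient-safety gap. A 21-day stop of all anti-inflammatory medication is put to both arms without qualification, and no visible section exempts or screens out patients who cannot safely pause such a drug taken for another condition.

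The conclusion rests on two assumptions: that the broad wording is meant as written, and that patients act on the request. The size in patients cannot be estimated from the documents and may be zero. The consent form is not judged. No sample-size or power figure changes. The point is worth acting on because the correction is small and the interruption is of the protocol's own making.

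**What to change.** 1. Add to 3.VI an exclusion along these lines: *patients who take an anti-inflammatory drug for another condition that, in the investigator's judgement (consulting the prescriber where needed), cannot safely be interrupted for the 21-day period around the procedure.*
2. Check it by asking about current medications when investigators first assess eligibility during office hours. This must come before consent and formal enrolment, before any drug is stopped and before an envelope is assigned. Neither the history taken after enrolment nor the concomitant-medication list, which has no stated timing, should serve as the check. Placed this way, no enrolled patient has to be withdrawn and none of the 50 places is used up.
3. Name the interruption of existing treatment as a risk in 5.I.

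The cost is one criterion, one question and one sentence. Some otherwise eligible patients, number unknown, will be excluded, so recruitment may be slightly slower.

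If the sponsor would rather keep these patients, the plan can let medically necessary drugs continue and record their use. That also meets the safety concern, but gives up the washout in those patients.
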